4.3 Concomitant Medications/Treatments

4.3.1 Acceptable Concomitant Medications

All treatments that the investigator considers necessary for a subject's welfare may be administered at the discretion of the investigator in keeping with the community standards of medical care. The use of any natural/herbal products or other traditional remedies should be discouraged, but use of these products, as well as any medication or vaccine including over-the-

counter or prescription medicines, vitamins, and/or herbal supplements that the patient is receiving at the time of enrolment or receives during the study must be recorded along with reason for use, dates of administration including start and end dates, dosage information including dose and frequency. If changes occur during the trial period, documentation of drug dosage, frequency, route, and date will also be included on the CRF.

Anti-emetics/Anti-diarrhoeals

Should a patient develop nausea, vomiting and / or diarrhoea, then these symptoms should be reported as AEs (see section 8.3) and appropriate treatment of the event given.

Subjects with ER+/PR+ disease may be given endocrine therapy.

Specifically, subjects using bisphosphonates or anti-RANKL mAb who were receiving this medication prior to study start, may continue receiving the medication during the study. However, a need to initiate this therapy during the conduct of this trial will be the equivalent of clinical disease progression and the subject must discontinue study treatment.

All concomitant medications received within 30 days before the first dose of pembrolizumab through the Safety Follow-up Visit should be recorded. After the Safety Follow-up Visit record all medications taken for SAEs and ECIs as defined in Section 6.3.2.

4.3.2 Prohibited Concomitant Medications

Subjects are prohibited from receiving the following therapies during the Screening, Treatment and Second Course Phases of this trial (unless otherwise noted below):

- Antineoplastic systemic chemotherapy or biological therapy not specified in this protocol.
- Immunotherapy not specified in this protocol
 - Subjects with HER2+ disease will be required to discontinue trastuzumab (Herceptin).
- Chemotherapy not specified in this protocol
- Investigational agents other than pembrolizumab
- Non-palliative radiation therapy (radiation that's considered palliative in nature as determined by treating investigator is allowed).
- Live vaccines or live-attenuated vaccines within 30 days prior to the first dose of pembrolizumab and while participating in the trial. Administration of killed vaccines is allowed.
- Initiation of bisphosphonate or anti-RANKL mAb (Treatment and Second Course Phases).

Subjects who, in the assessment by the investigator, require the use of any of the aforementioned treatments for clinical management should be removed from the trial. Subjects may receive other medications that the investigator deems to be medically necessary.

Restricted concomitant medications

Medication/class of drug:	Usage (including limits for duration permitted and special situations in which it's allowed):

Restricted concomitant medications

Usage (including limits for duration permitted and Medication/class of drug: special situations in which it's allowed):

Strong CYP3A inhibitors: itraconazole, telithromycin, clarithromycin, boosted protease inhibitors, indinavir, saquinavir, nelfinavir, boceprevir, telaprevir

Moderate CYP3A inhibitors: ciprofloxacin, erythromycin, diltiazem, fluconazole, verapamil

Strong or moderate CYP3A inhibitors should not be taken with olaparib. If there is no

suitable alternative concomitant medication then the dose of *olaparib* should be reduced for the period of concomitant administration. The dose reduction of olaparib should be recorded in the CRF with the reason documented as concomitant CYP3A inhibitor

- Strong CYP3A inhibitors reduce the dose of olaparib to 100 mg twice daily for the duration of concomitant therapy with the strong inhibitor and for 5 half lives afterwards.
- Moderate CYP3A inhibitors reduce the dose of olaparib to 150 mg twice daily for the duration of concomitant therapy with the moderate inhibitor and for 3 half lives afterwards.
- After the washout of the inhibitor is complete, the olaparib dose can be re-escalated.

Strong inducers: phenobarbital, phenytoin, rifampicin, rifabutin, rifapentine, carbamazepine, nevirapine, enzalutamide and St John's Wort

Moderate CYP3A inducers: bosentan, efavirenz and modafinil Strong or moderate CYP3A inducers should not be taken with olaparib. If the use of any strong or moderate CYP3A

inducers are considered necessary for the patient's safety and welfare this could diminish the clinical efficacy of olaparib. If a patient requires use of a strong or moderate CYP3A inducer then they must be monitored carefully for any change in efficacy of olaparib.

Restricted concomitant medications

Medication/class of drug:	Usage (including limits for duration permitted and special situations in which it's allowed):					
CYP3A4 substrates: hormonal contraceptive, simvastatin, cisapride, cyclosporine, ergot alkaloids, fentanyl, pimozide, sirolimus, tacrolimus and quetiapine CYP2B6 substrates: bupropion, efavirenz OATP1B1substrates: bosentan, glibenclamide, repaglinide, statins and valsartan	Effect of olaparib on other drugs Based on limited in vitro data, olaparib may increase the exposure to substrates of CYP3A4, OATP1B1, OCT1, OCT2, OAT3, MATE1 and MATE2K. Based on limited in vitro data, olaparib may reduce the exposure to substrates of 2B6. Caution should be observed if substrates of these isoenzymes or transporter proteins are co-administered.					
OCT1, MATE1 and MATE2K substrates: metformin						
OCT2 substrates: serum creatinine						
OAT3 substrates: furosemide, methotrexate						
Anticoagulant therapy	Patients who are taking warfarin may participate in this trial; however, it is recommended that international normalised ratio (INR) be monitored carefully at least once per week for the first month, then monthly if the INR is stable. Subcutaneous heparin and low molecular weight heparin are permitted.					
Palliative radiotherapy	Palliative radiotherapy may be used for the treatment of pain at the site of bony metastases that were present at baseline, provided the investigator does not feel that these are indicative of clinical disease progression during the study period. Study treatment should be discontinued for a minimum of 3 days before a patient undergoes therapeutic palliative radiation treatment. Study treatment should be restarted within 4 weeks as long as any bone marrow toxicity has recovered.					
Administration of other anti-cancer agents	Patients must not receive any other concurrent anti-cancer therapy, including investigational agents, while on study treatment. Patients may continue the use of bisphosphonates or denosumab for bone disease and corticosteroids for the symptomatic control of brain metastases provided the dose is stable before and during the study and they were started at least 4 weeks prior to beginning study treatment.					

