Combining PARP inhibitors and immunotherapy is a current treatment tested in several studies and tumor types. Rationale derives from the observation that PARP inhibitors enhanced cancer's ability to produce PD-L1 which enhances the efficacy of immunotherapy (Pd-1 and PDL1 inhibitors). In clinical studies tolerability of the combination is very good with no overlapping toxicities [25-28]. Due to evidence of combinatorial efficacy with the combination, patients previously exposed to PARP inhibitors will remain eligible as the patients PARP inhibitors naïve.

Patients with ER+ disease benefit from continuous hormonal inhibition. Studies show that combination therapy with PARP inhibition and anti-estrogens is safe and there are no interactions [29-30]. Therefore, this study will allow continuation of anti-estrogen therapy for patients with ER+ disease. While there is pre-clinical data on the combination of PARP inhibition and trastuzumab antitumor activity in HER2+ disease [31], due to a lack of safety data, subjects with HER2+ disease will be required to discontinue trastuzumab therapy.

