3.0 PATIENT ELIGIBILITY

3.1 Inclusion Criteria

- 3.1.1 Be willing and able to provide written informed consent/assent for the trial
- **3.1.2** Be ≥18 years of age on day of signing informed consent
- 3.1.3 Advanced BRCA-mutated and/or HDR-defect breast cancer progressing on or after prior therapy for metastatic disease or locally advanced disease; Prior therapy is defined as follows: for triple negative breast cancer progressing after at least 1 line of any prior chemotherapy; for HER2 positive disease must have progressed after at least two HER2 directed therapies in the metastatic setting including ado-trastuzumab emtansine (T-DM1); for hormone receptor positive disease (ER, PR, or both) must have progressed after a CDK4/CDK6 inhibitor plus hormonal therapy. Patients with progression within 12 months from previous neoadjuvant or adjuvant treatment could be enrolled in the study as 1st line therapy in metastatic setting.
- 3.1.4 Measurable disease by RECIST 1.1, with at least one lesion, not previously irradiated, that can be accurately measured at baseline as ≥ 10 mm in the longest diameter (except lymph nodes which must have short axis ≥ 15 mm) with computed tomography (CT) or magnetic resonance imaging (MRI) and which is suitable for accurate repeated measurements. Patients with non-measurable bone metastases in addition to measurable disease are eligible; however patients with non-measurable bone disease as the only site(s) of disease are not eligible.
- **3.1.5** ECOG 0 or 1
- **3.1.6** Documented BRCA deleterious germline or somatic mutation *AND/OR* HDR-defect.
- **3.1.7** FFPE tumor tissue available for analysis
- **3.1.8** Adequate organ function as defined in Table 1

Table 1 Adequate Organ Function Laboratory Values

System	Laboratory Value		
Hematological			
Absolute neutrophil count (ANC)	$\geq 1500/\mu L$		
Platelets	$\geq 100~000/\mu L$		
Hemoglobin	$\geq 10.0 \text{ g/dL or} \geq 5.6 \text{ mmol/L}^a$, with no blood		
	transfusion in the past 28 days		
Renal			
Creatinine OR	≤1.5 × ULN OR		
Measured or calculated ^b creatinine clearance	≥51 mL/min for participant with creatinine		
(GFR can also be used in place of creatinine or	levels >1.5 × institutional ULN		
CrCl)			
Hepatic			
Total bilirubin	≤1.5 ×ULN OR direct bilirubin ≤ULN for		
	participants with total bilirubin levels		
	>1.5 × ULN		

AST (SGOT) and ALT (SGPT)	≤2.5 × ULN (≤5 × ULN for participants with liver metastases)
Coagulation	

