3.2 Exclusion Criteria

- **3.2.1** Is currently participating or has participated in a study of investigational agent or using an investigational device with 30 days of the first dose of pembrolizumab.
- **3.2.2** a. Has had prior chemotherapy, targeted small molecule therapy, or radiation therapy within 3 weeks prior to study Day 1
 - b. Subjects must have recovered (i.e., \leq Grade 1 or at baseline) from any adverse events due to a previously administered agent. Subjects with \leq Grade 2 neuropathy are an exception to this criterion and may qualify for the study.
 - c. If subject received major surgery, they must have recovered adequately from the toxicity and/or complications from the intervention prior to starting therapy.
- **3.2.3** Is receiving systemic steroid therapy within three days prior to the first dose of pembrolizumab or receiving any other form of immunosuppressive medication
- **3.2.4** Is expected to require any other form of systemic or localized antineoplastic therapy while on trial.
 - Subjects with ER+/PR+ disease may be given endocrine therapy.
 - Subjects with HER2+ disease will be required to discontinue trastuzumab (Herceptin).
- **3.2.5** Has participated in another MK03475 trial.
 - **3.2.5.1** Note: Patients with or without prior PARP-inhibitor exposure may be included.
- 3.2.6 Concomitant use of known strong CYP3A inhibitors (eg. itraconazole, telithromycin, clarithromycin, protease inhibitors boosted with ritonavir or cobicistat, indinavir, saquinavir, nelfinavir, boceprevir, telaprevir) or moderate CYP3A inhibitors (eg. ciprofloxacin, erythromycin, diltiazem, fluconazole, verapamil). The required washout period prior to starting olaparib is 2 weeks.
- 3.2.7 Concomitant use of known strong (eg. phenobarbital, enzalutamide, phenytoin, rifampicin, rifabutin, rifapentine, carbamazepine, nevirapine and St John's Wort) or moderate CYP3A inducers (eg. bosentan, efavirenz, modafinil). The required washout period prior to starting olaparib is 5 weeks for enzalutamide or phenobarbital and 3 weeks for other agents.

- **3.2.8** Major surgery within 2 weeks of starting study treatment and patients must have recovered from any effects of any major surgery.
- **3.2.9** Has known hypersensitivity to pembrolizumab or any of its excipients

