4.0 TREATMENT PLAN

4.1 Treatment Dosage and Administration

This is an open-label, single-arm pilot study in 20 subjects with advanced BRCA mutation or HDR-defect associated breast cancer having progressed through standard first line therapy.

The study participation is up to 35 administrations of pembrolizumab (approximately two years).

Pembrolizumab and olaparib will be supplied by Merck.

Pembrolizumab will be administered at a dose of 200mg as a 30 minute IV infusion Q3W. Effort should be made to target infusion timing to be as close to 30 minutes as possible. However, given the variability of infusion pumps, a window of -5 minutes and +10 minutes is permitted (i.e., infusion time is 30 minutes: -5 min/+10 min).

Olaparib 300mg will be self-administered orally twice daily. The dose of olaparib used in this study is 300 mg twice daily which is the currently approved dose. Subjects will complete a compliance diary throughout the study treatment period. Olaparib tablets should be taken at the same time each day, approximately 12 hours apart with one glass of water. The tablets should be swallowed whole and not chewed, crushed, dissolved or divided. Olaparib tablets can be taken with or without food. Each container will be labelled in accordance with Good Manufacturing Practice (GMP) Annex 13 and per country regulatory requirement. If vomiting occurs shortly after the olaparib tablets are swallowed, the dose should only be replaced if all of the intact tablets can be seen and counted. Should any patient enrolled on the study miss a scheduled dose for whatever reason (e.g., as a result of forgetting to take the tablets or vomiting), the patient will be allowed to take the scheduled dose up to a maximum of 2 hours after that scheduled dose time. If greater than 2 hours after the scheduled dose time, the missed dose is not to be taken and the patient should take their allotted dose at the next scheduled time.

The Pharmacy Manual contains specific instructions for pembrolizumab dose calculation, reconstitution, preparation of the infusion fluid, and administration.

Table 2. Trial Intervention

Drug Dose/Potency	Dose/	Route of	Regimen/ Treatment
-------------------	-------	----------	--------------------

		Frequency	Administration	Period
Pembrolizumab	200 mg	Q3W	IV infusion	Day 1 of each cycle
Olaparib	300mg	BID	PO	Continuous; dispensed
				each cycle day 1 (each
				cycle=3 weeks)

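### The protocol both permits and bars endocrine therapy on study, and the analysis has no rule for a newly started or switched agent, whose benefit would count toward the 6-of-20 decision

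*Combined protocol and SAP*

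**What the plan says.** Four places bear on endocrine therapy.

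- **Section 3.2, exclusion 3.2.4.** Patients expected to need other antineoplastic therapy are excluded. Directly beneath stands: "Subjects with ER+/PR+ disease may be given endocrine therapy". No agent, start date or stable-dose condition is attached.
- **Section 4.3.1.** The same permission is repeated among the acceptable medications, again without conditions.
- **Section 1.1.** The rationale says: "Therefore, this study will allow continuation of anti-estrogen therapy for patients with ER+ disease". It does not mention starting a new agent.
- **Section 4.3.2, restricted-medications table.** "Patients must not receive any other concurrent anti-cancer therapy, including investigational agents, while on study treatment". The same row lets patients stay on bone agents, and on corticosteroids for brain metastases, "provided the dose is stable before and during the study and they were started at least 4 weeks prior to beginning study treatment". Endocrine therapy is not listed there.

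The washout in exclusion 3.2.2 reads: "Has had prior chemotherapy, targeted small molecule therapy, or radiation therapy within 3 weeks prior to study Day 1". It does not name endocrine therapy.

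On the design, section 4.1 states: "This is an open-label, single-arm pilot study in 20 subjects with advanced BRCA mutation or HDR-defect associated breast cancer". Section 9.2 counts complete response, partial response, or stable disease of at least four months as clinical benefit. The trial stops if 2 or fewer of the first 10 patients benefit, and rejects a 15% rate if 6 or more of 20 do. Sections 9.1 to 9.3 contain no rule for a patient who starts or changes endocrine therapy.

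**The concern.** A site that follows 3.2.4 and 4.3.1 may start a new endocrine agent at or after entry. A site that follows the table in 4.3.2 may not. The text does not say which governs.

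A switch is foreseeable. Under inclusion 3.1.3, "for hormone receptor positive disease (ER, PR, or both) must have progressed after a CDK4/CDK6 inhibitor plus hormonal therapy", apart from patients who enter through the route for progression within 12 months of neoadjuvant or adjuvant treatment. Such a patient has progressed on or after one hormonal regimen and could be moved to another.

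With no control arm, disease control produced by the added drug cannot be separated from that of pembrolizumab plus olaparib. Stable disease of four months is probably the more exposed part of the decision endpoint, but the response rate, which is the primary objective, is affected too. What is at stake is the 5% false-positive rate stated for the go/no-go rule.

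**Working it through.** **Step 1: the plan's own figures.** Inputs from section 9.2: 10 patients in stage 1, stop at 2 or fewer; 20 in total, reject at 6 or more; null rate 0.15, alternative 0.41. With X1 and X2 the numbers with benefit in each stage of 10, the exact rejection probability at true rate p is

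P(reject) = Σ over k = 3…10 of P(X1 = k) × P(X2 ≥ 6 − k).

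| | Recomputed | Stated |
|---|---|---|
| P(reject) at p = 0.15 | 0.0498 | 5% |
| P(reject) at p = 0.41 | 0.806 | 80% |
| Early stop at p = 0.15 | 0.820 | 0.82 |
| Early stop at p = 0.41 | 0.152 | 0.16 |

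The design reproduces; the last difference is 0.8 percentage points and has no bearing here.

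**Step 2: the passages side by side.**

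| Question | 3.2.4 and 4.3.1 | 1.1 | Table in 4.3.2 |
|---|---|---|---|
| Ongoing endocrine therapy kept? | Yes | Yes | No exception given |
| New agent started or switched? | Not excluded | Not addressed | No exception given |

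The conflict is between the first and last columns. Section 1.1 conflicts with neither answer in the first column. For bone agents the protocol does draw the line: sections 4.3.1 and 4.3.2 allow prior users to continue but prohibit starting, and 4.3.1 treats a need to start as clinical progression. For endocrine therapy no such line is drawn.

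**Step 3: sensitivity of the false-positive rate.** Suppose the combination itself stays at the null rate of 0.15. Let

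- e = share of ER+ patients. Assumed 14/30 = 0.467, from the primary-tumour series in section 1.1.
- u = share of ER+ patients who start or switch an agent. Not in the documents; shown at 10%, 25%, 50% and 100%.
- a = share of those users who gain benefit and would otherwise have had none. Not in the documents; shown at 0.1, 0.2 and 0.3.

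The observed benefit rate becomes p = 0.15 + e × u × 0.85 × a. For example, u = 0.5 and a = 0.3 give p = 0.15 + 0.467 × 0.5 × 0.85 × 0.3 = 0.2095. Putting p into the Step 1 formula:

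| Uptake u | Rate p for a = 0.1 to 0.3 | P(reject), a = 0.1 | a = 0.2 | a = 0.3 |
|---|---|---|---|---|
| 0 | 0.150 | 0.0498 | 0.0498 | 0.0498 |
| 10% | 0.154–0.162 | 0.0555 | 0.0615 | 0.0679 |
| 25% | 0.160–0.180 | 0.0647 | 0.0820 | 0.1018 |
| 50% | 0.170–0.210 | 0.0820 | 0.1241 | 0.1756 |
| 100% | 0.190–0.269 | 0.1241 | 0.2352 | 0.3709 |

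The stage 1 safeguard weakens as well: at u = 50% and a = 0.3 the probability of stopping early falls from 0.820 to 0.649.

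**The case against.** The strongest defence is that a specific permission, stated twice, is naturally read as overriding a general bar. In 3.2.4 the permission sits directly under a general prohibition, as an exception to it. The summary of changes attributes text in section 4.3 to incorporated olaparib template language, so the table row may simply lack a cross-reference. This is a fair account of how the conflict may have arisen, and it could settle whether endocrine therapy is allowed at all. It does not settle whether a new agent may be started, nor how such a patient is counted. If the bar governs instead, new agents would not be started and the attribution problem would not arise; the text does not say that either.

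A reader might infer that section 1.1 restricts endocrine therapy to continuation, giving three competing policies. The documents do not support that. The sentence allows continuation without excluding anything else, it is background rationale, and continuing an agent falls within the wider permission.

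A reader might also take 0.124–0.371 as the expected false-positive range. That range needs every ER+ patient to start a new agent, which nothing in the documents suggests. The 47% is also borrowed: it comes from untreated primary tumours of germline BRCA carriers, while the trial enrols pretreated advanced disease and includes somatic BRCA and HDR-defect tumours.

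It is also true that the problem is partly recoverable. Section 4.3.1 requires concomitant medications and their dates to be recorded, and section 9.3.3 provides for group comparisons of binary outcomes. But endocrine use is not named there, and at 20 patients any such split can only describe.

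**Conclusion.** The concern holds as a conflict in current text plus a missing counting rule. The permission in 3.2.4 and 4.3.1 cannot be reconciled with the table in 4.3.2 as written. Under the permission, benefit arising on a newly started or switched endocrine agent counts toward 6 of 20.

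The size depends on uptake, which the documents do not give. On the stated assumptions, the nominal 0.050 becomes about 0.055–0.068 at 10% uptake among ER+ patients, 0.065–0.102 at 25% and 0.082–0.176 at 50%; 0.124–0.371 is the limiting case of full uptake. The direction is upward in every scenario where the added agent helps anyone. If no patient starts or switches an agent, there is no inflation from this source. The need to reconcile the text does not depend on any of these figures. Which clinical rule is right is not judged here.

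**What to change.** 1. **Reconcile the text.** Bring section 1.1, exclusion 3.2.4, section 4.3.1 and the table in 4.3.2 into one rule that says whether endocrine therapy is permitted and, if so, whether that covers starting or switching. The choice is for the clinical team.
2. **Add a counting rule to section 9.** For analysis, treat an endocrine agent started or switched after C1D1 as new anti-neoplastic therapy. A response or stable disease first reached after that date does not count, and time in stable disease after that date does not count toward the four months. Section 4.6 already uses the start of new anti-neoplastic therapy as an end point for collecting disease status.
3. **Flag recent starts.** A cut at C1D1 alone misses a switch made just before it, which the three-week washout does not cover. Flag agents first started in the 30 days up to the first dose; section 4.3.1 already requires medications from that window to be recorded.
4. **Report both ways.** Give the response rate and the clinical benefit rate with and without patients on new or switched endocrine therapy, labelled descriptive.

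The cost is wording and one derived variable from data already collected. The reported rate may be lower, and with 20 patients the split will not support a formal comparison.
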